COVER PAGE

Pre-op Cognitive Behavior Therapy to Decrease Chronic Post-Surgical Pain in TKA

NCT04814992

November 23, 2020

PRINCIPAL INVESTIGATORS: [name] & [name], PhD, FAAN

PROTOCOL TITLE: Pre-op CBT to Reduce the Risk for Development of Chronic Post-surgical Pain in Patients undergoing Total Knee Arthroplasty

INTRODUCTION AND PURPOSE:

A significant number of patients develop chronic post-surgical pain following knee joint replacement surgery, and the risk factors for this problematic outcome have been identified. Proposed is the development and preliminary efficacy testing of a novel computer-assisted cognitive behavioral intervention integrating opioid taper delivered in the four weeks prior to surgery to address these risk factors, with the expectation that both the severity of post-operative pain and the subsequent incidence of chronic post-surgical pain will be reduced. In that chronic post-surgical pain brings with it diminished functionality and quality of life, ongoing opioid use, and direct patient costs, it is critical that interventions aimed at mitigating its development are implemented and evaluated in the clinical setting.

OBJECTIVES:

In a sample of adult men and women with chronic pain, on opioid therapy and undergoing a planned TKA, the objectives of this randomized clinical trial are to:

1. Add a motivational interviewing component to a validated computer-assisted CBT intervention for chronic pain (PAINTrainer) to encourage opioid tapering in the 4 weeks prior to surgery.
2. Describe the efficacy of the 4-week targeted pre-operative CBT intervention in 75 TKA patients to decrease preoperative chronic pain severity, preoperative opioid consumption, and symptoms of depression, anxiety and pain catastrophizing prior to surgery in comparison to 75 TKA patients randomized to treatment-as-usual.
3. Describe the effects of a 4-week targeted pre-operative CBT intervention in 75 TKA patients on 72hr post-operative pain severity, and 3- and 6-month rates of CPSP in comparison to 75 TKA patients randomized to treatment-as-usual.

BACKGROUND:

Knee Joint Replacement and Chronic Post-surgical Pain

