Pain catastrophizing – Pain catastrophizing will be measured by the Pain Catastrophizing Scale (PCS).⁵³ The PCS is a 13-item self-report scale, with each item rated on a 5-point scale: 0 (Not at all) to 4 (all the time). It is broken into three subscales (magnification, rumination, and helplessness); results from the initial development and validation studies indicate that the PCS is a reliable and valid measurement tool for catastrophizing in clinical and non-clinical populations. PCS will be completed prior to and following completion of the intervention and at the 3- and 6-month follow ups to assess the durability of the intervention.

Depression and Anxiety - To measure symptoms of depression and anxiety, the PROMIS® (Patient-Reported Outcomes Measurement Information System) person-centered measures will be utilized.⁵⁴ Specifically, the 8-item PROMIS depression and anxiety short forms will be compared prior to and following completion of the intervention; to evaluate the stability of CBT skills, the PROMIS will also be administered at 3 and 6 months.

Potential confounders – Pre-existing medical comorbidities or post-operative complications may affect surgical outcomes with respect to pain severity and resolution. To account for the effects of these confounders, all medical comorbidities will be extracted from the EHR by the study coordinator prior to surgery and recorded in the study database. Also added to the study database will be any unanticipated adverse events following surgery, and with medical comorbidities, considered as moderators of the effects of the intervention on the development of CPSP.

Post-operative pain intensity – Severity of post-operative pain will be operationalized as (1) responses on a visual analogue pain scale (VAS) and (2) consumption of opioid analgesic medications during the first 72 hours following surgery. The VAS ranges from 0 (no pain) to 10 (worst pain imaginable), and pain scores are collected every 4 hours as part of routine practice. Pain ratings will be graphed over time and area under the curve calculated. Dose of opioid analgesics consumed during this period (24hr increments and total) will be abstracted from the electronic health record and converted into MEDD for analysis.

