Chronic post-surgical pain – To evaluate for the presence of CPSP, subjects will be asked at 3- and 6-months if they have pain in the surgical site that developed or increased in intensity following the surgery utilizing a checklist based upon the IASP definition of CPSP (Appendix). If they respond affirmatively, BPI pain scores will be collected to assess the intensity and interference associated with the CPSP. In addition, subjects will be asked if they are continuing to use opioids at these timepoints, and if so, daily MEDD calculated for analysis.

2. Group Modifications:

The only group modification with respect to measures is that only those in the intervention group will participate in the survey assessing subject satisfaction with the intervention.

3. Method for Assigning Subjects to Groups:

A randomization scheme will be generated by the study biostatistician and provided to the study coordinator who will assign consecutively enrolled subjects to group.

4. Administration of Surveys and/or Process:

The data collection schedule is described below:

	Baseline (T-4weeks)	Pre-operation (T0)	Post-operation (T = 72hr)	Follow-up (T + 3 and 6 months)
Chronic Pain Intensity (BPI)	X	X		X
Opioid Use (MEDD)	X	X		X
PDMP review	X			X
Pain Catastrophizing (PCS)	X	X		X
Depression & Anxiety symptoms (PROMIS)	X	X		X
CBT use, adherence, satisfaction ^a		X		
Post-operative Pain Severity (72hr VAS)			X	
Post-operative Pain Severity (72hr MEDD)			X	
Chronic post-surgical pain checklist				X

^a subjects in treatment group only

5. Data Management:

Collected data will be entered into the U Penn School of Nursing REDCap (Research Electronic Data Capture) system by trained CITI- and HIPAA-certified research assistants, which is a central and secure resource for data processing and management. As the front-end collection instrument is created, REDCap automatically creates a database designed to store the data that will be recorded from the research. The U Penn School of Nursing has licensed its own version of REDCap that is housed on password protected servers located within a data center inside the School of Nursing firewall, and therefore are afforded the same network protections as other sensitive clinical systems. REDCap was developed specifically around HIPAA-Security guidelines with features such as data encryption and is recommended to Penn researchers by our Office of Human Research.

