session before completing it and resume where they left off, and access program resources to manage goals and reminders, log practices, review progress in easy-to-read graphs, read about others' experiences using the skills, and share their own. In addition, they will have access to PAINTrainer for one-month post operatively to reinforce the basic CBT principles; the program also tracks participants' use. Although it is recommended to complete one session per week, in this application patients will be asked to complete 2 sessions per week for four weeks; the developers of the PAINTrainer (consultants [name] and [name]) note that the efficacy of flexible approaches, including shortening of the delivery schedule.

In addition to the PAINTrainer, we will integrate a motivational interviewing (MI) intervention delivered by a trained "coach" across the sessions about (1) the benefits of opioid tapering for post-operative pain control, (2) approaches for safely tapering, (3) identifying and managing withdrawal symptoms patients may experience. Co-PI [name] will provide scripted language and train the study coordinator to effectively deliver this education within the CBT context employing MI techniques, and monitor fidelity to the delivery at regular intervals over the course of the study. The content and tapering guidelines will be based upon the US Department of Veterans Affairs Pain Management Opioid Taper Decision Tool⁵⁵ which provides guidance on dose reduction schedules, over-the-counter medications to treat mild withdrawal symptoms, and resources to manage discomfort or distress. Patients will not be expected to taper completely off opioids during the intervention period, but up to 30% reduction in daily opioid dose is anticipated. For future testing, the MI intervention will be integrated into the platform virtual coach, however it is cost-prohibitive to do so in the current application.

Treatment as usual: Patients scheduled to undergo total joint arthroplasty at the study site are automatically enrolled in a mandatory 4-hour education class delivered by a nurse educator or physical therapist. Utilizing an in-person PowerPoint presentation format, patients are informed about pre-habilitation exercises to do prior to surgery; what to expect the day of surgery; the multimodal analgesia protocol used in the perioperative period; options for anesthesia and analgesia; and the expectation of physical therapy after surgery.

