Opioid taper: As a part of the intervention and with the guidance of their trained coach, one-half of the subjects will be encouraged to gradually taper their opioid use in the month prior to surgery. It is possible that in doing so, subjects may experience the uncomfortable symptoms associated with opioid withdrawal. To avoid the emergence of these, subjects will be instructed to taper their dose gradually (no more than 10%/week), and will be provided with information on how to self-manage these symptoms should they arise. In addition, subjects will be instructed to contact their coach should the symptoms become severe, to receive guidance on how to temporarily cease and then restart taper attempts. In that subjects will have been regular users of opioids for at least three months prior to study enrollment, they will have developed a certain degree of physiologic tolerance, offering protection against any respiratory depressant effects during a taper pause.

Breach of Confidentiality: Participation in this study may constitute a social risk to the participant in that others may learn that he or she has chronic pain and is taking opioid medications. Due to the sensitive nature of this information, privacy and confidentiality will be strictly maintained in all aspects of participation. Consent and data collection sessions will take place in private rooms where strict privacy is enforced and all staff are HIPAA certified.

Acute Anxiety or Depressive Symptoms: It is possible that the opioid taper for the intervention group, or the upcoming surgery for both groups may precipitate unanticipated symptoms of acute anxiety or depression. As described below, co-PI [name] is a licensed clinical psychologist with over 40 years' experience in treating patients with chronic pain, will be available to assess and intervene with patients who experience these distressing symptoms during the pre-operative period.

2. Benefits:

The potential benefit for both the participants and broader segments of society is to improve pain outcomes following a very common procedure, TKA, ideally decreasing the severity of post-operative pain experienced and

the development of CPSP. Development of an effective intervention to address the risk factors for poor pain outcomes following TKA can guide clinical practice based upon evidence.

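### 72-hour opioid consumption is counted as post-operative pain severity although the intervention coaches one arm to lower its opioid dose, so a lower value could mean less opioid rather than less pain

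*Combined protocol and SAP*

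**What the plan says.** The instrument description for post-operative pain intensity (METHODS, 1. Study Instruments) gives two components. The first is the VAS, rated every 4 hours and summarised on its own: "Pain ratings will be graphed over time and area under the curve calculated". The second is "consumption of opioid analgesic medications during the first 72 hours following surgery", taken in 24-hour increments and in total and converted to MEDD. The schedule table (METHODS, 4. Administration of Surveys and/or Process) gives each its own row, and the opioid row is labelled "Post-operative Pain Severity (72hr MEDD".

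The intervention acts on opioid dose. Objective 1 adds a motivational interviewing component "to encourage opioid tapering in the 4 weeks prior to surgery". Under STUDY PROCEDURES (Pre-operative CBT Intervention) the coach covers "the benefits of opioid tapering for post-operative pain control", and "up to 30% reduction in daily opioid dose is anticipated". The control arm gets the usual education class, whose description mentions no taper. Everyone enters on an MEDD above 50 mg (Key Inclusion Criteria).

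The Statistical Analysis section models group by time (72 hours, 3 months, 6 months) for Objective 3. It does not name the 72-hour variable, and its covariate rule refers to baseline factors. The documents do not separate continuing home opioid from opioid taken for surgical pain, and they do not say how to read the results if VAS and MEDD disagree.

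**The concern.** Opioid consumption can stand in for pain when the treatments under comparison do not themselves act on opioid taking. Here one of them does, and in one arm only. Four explanations of a lower 72-hour MEDD in the CBT arm are then open: a lower habitual dose carried into the hospital stay, lower tolerance, reluctance to take opioids after four weeks of coaching, and less pain. Only the last is what the label claims.

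The stake is what Objective 3 can conclude. Pre-operative opioid consumption is already an Objective 2 outcome, so the taper effect could be reported a second time as an effect on post-operative pain. The BACKGROUND also treats post-operative pain severity as an independent predictor of CPSP, so a mislabelled result would blur the mechanism the trial wants to describe. The stated goal is reliable effect sizes for larger studies. An effect size for pain that is partly a dose difference would not serve it.

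**Working it through.** **Plan's own figure.** There is none to reproduce. The documents give no expected value, SD or power for 72-hour MEDD or 72-hour VAS. The sample size statement concerns chronic pain severity and does not bear on this point.

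**Inputs.**
- Entry dose D = 50 mg/day, the inclusion threshold. Actual doses lie above it, and the shift scales in proportion.
- Taper share r = 30%, the upper end of what is anticipated; 10% is taken as a smaller case.
- Window = 3 days.
- Carry-over c = the share of the home-dose difference that appears in the 72-hour total. This is not in the documents, so it is varied from 0 to 1.
- Pain is equal in both arms, and the control arm does not change its dose (assumptions).

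**Formula.** Shift in 72-hour MEDD = 3 × D × r × c.

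| r | c | Shift |
|---|---|---|
| 30% | 0 | 3 × 50 × 0.30 × 0 = 0 mg |
| 30% | 0.5 | 3 × 50 × 0.30 × 0.5 = 22.5 mg |
| 30% | 1 | 3 × 50 × 0.30 × 1 = 45 mg (150 to 105 mg) |
| 10% | 1 | 3 × 50 × 0.10 × 1 = 15 mg |

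At an assumed 100 mg/day the third row doubles to 90 mg.

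**Does baseline adjustment remove it?** No. Take two patients, one per arm, both on 50 mg/day at T-4 weeks. After a 30% taper their T0 doses are 35 and 50 mg/day. At the same baseline value the full carry-over difference is still 3 × (50 − 35) = 45 mg, because it arises after randomisation. Baseline adjustment can improve precision but cannot remove this difference.

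**Does expressing the total relative to T0 settle it?** Only in part. Subtracting 3 × T0 dose removes 105 mg in the CBT arm and 150 mg in the control arm. With full carry-over the 45 mg artefact disappears. With no carry-over the raw totals are equal, and the subtraction makes the CBT arm look 45 mg higher. T0 dose is also affected by treatment. The T0-relative figure is therefore useful as description and should not replace the total.

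**Could a shift of this size be declared significant?** With 75 per arm, two-sided alpha of 0.05 (sidedness is not stated) and an assumed SD, the probabilities for a 45 mg shift are about 79% at SD 100 mg and 28% at SD 200 mg. For 22.5 mg they are 28% and 10%; for 15 mg, 15% and 7%. The SDs are illustrations only.

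**The case against.** The strongest reply is that the plan does not rest on opioid dose alone. VAS comes first in the definition, has its own AUC and its own schedule row, and is never combined with MEDD. If dose fell with pain unchanged, the VAS result could show it. Elsewhere the two are already kept apart: the post-operative and data collection paragraphs under STUDY PROCEDURES, and the protected health information paragraph, list pain and opioid use as separate items. This stands. It limits the problem to the definition, the label and the missing reading rule.

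A reader might infer that the CBT arm will show lower 72-hour MEDD whatever its pain, and that a successful taper would be read as pain relief. The documents do not support that. They do not say how home opioids are handled in hospital, and with no carry-over the dose artefact is zero. The 30% figure is an upper end.

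A reader might also infer that 72-hour MEDD can never support a pain claim. That goes too far. The BACKGROUND argues that long-term opioid use heightens pain sensitivity, so a taper may truly reduce pain, and lower MEDD together with lower VAS would be consistent with that.

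Finally, VAS depends on how much opioid was taken. If patients take opioid until comfortable, a real difference in pain may show in consumption and not in VAS. This also stands, and it is why MEDD should be relabelled and kept beside VAS.

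**Conclusion.** The point holds as one of interpretation. By the plan's own definition and label, lower 72-hour opioid consumption counts as lower pain severity, while the tested intervention aims to lower opioid use in one arm. The measure alone cannot distinguish reduced habitual dose, tolerance or willingness to take opioids from reduced pain, and nothing in the analysis section resolves this.

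At a 50 mg/day entry dose and equal pain, the part due to habitual dose lies between 0 and 45 mg over 72 hours for a 30% taper. Where it falls depends on carry-over, which the documents do not give. Any effect of tolerance or coached reluctance is not quantified here.

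The stakes are modest. The primary outcome is chronic pain severity, Objective 3 is descriptive and contrasts are treated as exploratory. The change is still worthwhile, because it decides what a difference in 72-hour MEDD may be said to show.

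**What to change.** 1. In the instrument description and the schedule table, name VAS AUC as the measure of 72-hour pain severity. Relabel 72-hour MEDD as a separate opioid-use outcome.
2. In the Statistical Analysis section, analyse 72-hour MEDD adjusted for T-4 weeks MEDD, stating that this is for precision and does not remove a dose difference created by the taper. Also describe 72-hour MEDD relative to T0 MEDD.
3. Pre-specify that VAS and MEDD are reported and read together, and that lower MEDD without lower VAS is reported as lower opioid use, not as less pain.

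The cost is wording and a small amount of analysis. The schedule already lists MEDD at T0 without restricting it to one arm. The description of the pre-operative session mentions only the experimental group, so confirm that T0 MEDD is collected in controls as well.

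The downside is one fewer measure labelled as pain. Because VAS depends on opioid taken, some real pain differences may appear only in consumption, so MEDD must still be reported beside VAS.

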Total knee arthroplasty (TKA) is among the most common surgical procedures performed in the US^{1,2}, and as the population ages and face age-related joint deterioration, will only increase in frequency.^{3,4} Although in the majority of cases, patient-centered outcomes (pain, function and quality of life) are improved following this procedure, a significant number of patients develop chronic post-surgical pain (CPSP), which is often rated as severe, and includes treatment-resistant neuropathic components.⁵ The International Association for the Study of Pain defines CPSP as pain that develops or increases in intensity after a surgical procedure, persists beyond the tissue healing process (> 3months), and is localized to the surgical field or innervation territory of nerve located in surgical field.²⁴ Rates of CPSP are alarmingly high following TKA, with Petersen and colleagues^{6,7} reporting that between 44% to 53% patients develop CPSP, 15% to 19% of whom rate their pain as severe. Clearly, the development of CPSP following TKA is a significant adverse outcome, which brings with it decreased quality of life, diminished functionality, disability, and perhaps most concerning in the era of the opioid crisis, long-term opioid use.^{8,12} Further, CPSP is associated with notable economic burden, with recent analysis suggesting almost \$30,000 in annual adjusted indirect costs to patients per year, an amount directly related to the severity of CPSP pain.¹³

Preoperative Predictors of Chronic Post-surgical Pain

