Data quality will be monitored by random inspection of the completed datasets by the study coordinator and any problems detected will be discussed with the co-PIs. In addition, the PIs will carefully monitor the data accrual weekly. Data will be entered on an ongoing basis under the direction of the study coordinator, and weekly reports detailing health events, study progress, and data accuracy and completeness will be generated for review by the PIs and co-investigators. Quality assurance activities will be supervised by the study coordinator. Prior to analysis, missing data or discrepancies will be corrected by the project director based on source documents. The study's statistician will analyze the data, using SAS for Windows Version 9.4 statistical software.

Data monitoring of all aspects of this study will proceed in an exacting manner and meet all IRB requirements. Data will be collected by trained research staff using standardized hardcopy and electronic forms and will only be identified with a study ID. Personal identifiers required for follow-up will be linked with the study ID and kept confidential by Drs. [name] and [name] in a secured cabinet. No presentation or publication of the results of this study will refer to the individual participants or present information that would identify any participant. No data will be disclosed to personnel not listed on the study protocol.

6. Subject Follow-up:

Using contact information obtained at the baseline visit, subjects will be contacted via telephone at 3- and 6-months following surgery to determine if CPSP is present utilizing a checklist based upon the IASP definition of CPSP (Appendix). If present, the BPI will be administered, and any opioid use recorded and checked against the PDMP. In addition, the PCS and PROMIS measures will be collected to evaluate the durability of CBT training effects. The sample does not include transient groups, minimizing potential attrition.

STUDY PROCEDURES:

1. Detailed Description:

The study procedures, including all the visits, contacts, and interactions are described sequentially below:

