Appendix
Chronic Post-Surgical Pain (CPSP) Checklist

If Brief Pain Inventory indicates that patient still has pain:	
1. Did the pain develop or increase in intensity after the surgical procedure?	 YES  NO
2. Is the pain in the same location/area as the surgical procedure?	 YES  NO
3. Is the pain distinct from other kinds of pain that were present prior to the surgery?	 YES  NO  NA
4. Could your pain be described as burning, prickly, tingling, electric shocks and/or pins and needles?	 YES  NO
5. Is the skin covering your painful area more sensitive to touch?	 YES  NO

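### The CPSP checklist has no duration item, so the 3-month rate can include pain that has not lasted more than 3 months and the 6-month rate could include recent-onset pain

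*Combined protocol and SAP*

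**What the plan says.** The Background section on knee replacement and CPSP gives a definition with three elements. It must be "pain that develops or increases in intensity after a surgical procedure", it must be pain that "persists beyond the tissue healing process (> 3months"), and it must lie in the surgical field or the territory of a nerve there.

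Ascertainment is described under METHODS, 1. Study Instruments, where "subjects will be asked at 3- and 6-months if they have pain in the surgical site that developed or increased in intensity" after the operation, using a checklist said to rest on that definition. METHODS, 6. Subject Follow-up adds that "subjects will be contacted via telephone at 3- and 6-months following surgery to determine if CPSP is present utilizing a checklist"; the procedures section repeats this.

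The Appendix checklist opens with "If Brief Pain Inventory indicates that patient still has pain". Its items are:

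1. "Did the pain develop or increase in intensity after the surgical procedure"
2. "Is the pain in the same location/area as the surgical procedure"
3. whether the pain differs from pain present before surgery
4. neuropathic descriptors
5. skin sensitivity

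The plan states no call window, no rule for turning the five answers into a CPSP status, and no rule linking the two calls.

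The 3- and 6-month CPSP rates are outcomes of Objective 3. Target Population and Accrual calls their analysis exploratory and a source of effect sizes. The Statistical Analysis section makes dependable effect sizes for planning larger studies its main goal.

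**The concern.** One of the three defining elements of CPSP is missing from the instrument that classifies it. A patient can be scored as a case without meeting the plan's own definition, and nothing else on the call would reveal it.

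Two routes are open. At the first call, pain that has not yet lasted more than 3 months can score positive. At the second, surgical-site pain that began after month 3 could score positive.

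At stake is what the two rates mean. A later trial that takes its control rate or effect size from this one would be planning on an outcome that may differ from the defined condition. The answer cannot be reliably recovered afterwards if nobody asks about duration during the call.

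**Working it through.** **Definition against instrument**

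| Element (Background) | Question in Study Instruments | Appendix checklist |
|---|---|---|
| Arises or worsens after surgery | asked | item 1 |
| Lasts more than 3 months | not asked | none |
| In the surgical field | asked | item 2 |

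Items 3 to 5 concern distinctness, neuropathic quality and skin sensitivity. The checklist's lead-in relies on the BPI, whose intensity ratings (Study Instruments) are worst and least over 24 hours, average and current pain. None records onset or length.

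**First call.** Let t be the time from operation to call. Pain that arose or worsened after surgery has been present in that form for at most t. If t is 3 months or less, a duration above 3 months is impossible and any positive score fails the definition. If t is longer, the element can be met but is not checked. Without a window, t may fall on either side.

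**Second call.** Pain that starts d months after surgery has lasted 6 − d months at the call. Exceeding 3 months requires d below 3. Surgical-site pain with d between 3 and 6 can still be answered yes on items 1 and 2.

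**Size.** The plan states no figure for CPSP. Its one powered figure, 75 for a pre-post change in pain severity, reproduces: a paired t-test with standardised effect 0.33, two-sided 0.05 (sidedness assumed) and 80% power gives 74.02, so 75. This point does not depend on it.

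The following is an illustration only.

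- Control rate p_c: 44%, 53% and the midpoint (44 + 53)/2 = 48.5%, from the Background, which gives no time point for these rates.
- True risk ratio: 0.70, assumed, so p_t = 0.70 × p_c.
- f: share of patients without definition-CPSP who score positive, assumed.
- All true cases are assumed to score positive.

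Observed rate = p + f(1 − p). With equal f, the observed difference = (p_c − p_t)(1 − f). At 48.5% and f = 20%:

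- control: 0.485 + 0.2 × 0.515 = 0.588
- intervention: 0.3395 + 0.2 × 0.6605 = 0.4716
- difference: 0.1164 = 0.1455 × 0.8
- risk ratio: 0.80 instead of 0.70 (0.76 at f = 10%, 0.84 at f = 30%)

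With unequal shares, observed minus true difference = f_c(1 − p_c) − f_t(1 − p_t). The difference is enlarged when f_t/f_c is below (1 − p_c)/(1 − p_t). That threshold is 0.515/0.6605 = 0.78 at 48.5%, 0.56/0.692 = 0.81 at 44% and 0.47/0.629 = 0.75 at 53%. Taking f_c = 20% and f_t = 14% (ratio 0.70) at 48.5%, the intervention rate is 0.3395 + 0.14 × 0.6605 = 0.432. The difference is 0.588 − 0.432 = 0.156 and the risk ratio 0.73.

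Risk difference in percentage points:

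| Control rate | True | f = 10% both | f = 20% both | f = 30% both | 20% control, 14% intervention |
|---|---|---|---|---|---|
| 44% | 13.2 | 11.9 | 10.6 | 9.2 | 14.7 |
| 48.5% | 14.6 | 13.1 | 11.6 | 10.2 | 15.6 |
| 53% | 15.9 | 14.3 | 12.7 | 11.1 | 16.5 |

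This table cannot describe a first call at or before 3 months, where the literal definition leaves no true cases. It bears on the 6-month call, or on a first call made after 3 months.

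**The case against.** **The lead-in says the patient still has pain.** This is persistence wording, and it fits pain from a recent fall poorly. But it draws on BPI ratings that carry no duration, and every participant had chronic pain before surgery, so still having pain does not date the post-surgical component. Study Instruments and Subject Follow-up also place the BPI after a positive checklist, so the order of the two is itself unsettled.

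**A call at 3 months sits on the boundary.** The definition ties the end of healing to 3 months, so a call at that time may miss by days only. Calls before 3 months are a possibility, not something the plan schedules. This stands and limits the point. Item 1 also excludes resolving pain that is neither new nor worse than before surgery.

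**The repeated checklist identifies pain present at both calls.** It does, and adverse events after surgery are recorded and considered as moderators. But no rule uses either to define a case.

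**The scoring is inferred.** Partly true: the Study Instruments question matches items 1 and 2, but the role of item 3 is unstated. That is a further reason to write a rule.

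**False positives would dilute the effect.** A reader might infer this because both arms use the same checklist. It requires equal false-positive shares. The intervention is expected to lessen post-operative pain too, so it may also lessen lingering pain; the unequal case above enlarges the risk difference.

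**The analysis is exploratory and will be read with caution.** Correct, and it lowers the weight of the point. Effect sizes are nevertheless the declared purpose of the analysis.

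**Moving the call by a few weeks will not separate healing from chronic pain.** Largely true. The change brings the outcome into line with the plan's own 3-month boundary; it does not validate that boundary.

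**Conclusion.** The point holds as a mismatch between definition and instrument. Followed exactly, the plan can score as CPSP pain that fails its own duration element. The 3-month result is the more exposed, because that element can hardly be met at a call made at 3 months. The 6-month route is only a possibility left open by the missing rule.

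A reader might go further and conclude that the reported rates will in fact be made up of healing or recent pain, or that the between-arm difference will be diluted. The documents support neither. They give no misclassification share and no basis for assuming it equal across arms. The risk ratio of 0.70 and every value of f above are assumptions, and the results run in both directions. What can be said is that case status, and so the effect size handed on to larger studies, is not tied to the stated definition. For an exploratory outcome this is a moderate issue, worth correcting because it is nearly free.

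**What to change.** Add one yes/no item to the checklist: has the surgical-site pain been present, continuously or recurrently, for more than 3 months since the operation? State a scoring rule in which CPSP is positive only if this item and items 1 and 2 are all answered yes.

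For the first call, choose one of two options:

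- open the window only after 3 full months, for example weeks 14 to 16; or
- keep the call at 3 months, report the result as surgical-site pain at 3 months, and reserve the term CPSP for the 6-month result.

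Both changes should be in place before follow-up calls begin. The cost is one extra question on an existing call, a slightly later first call under the first option, and a somewhat lower event rate. The 6-month call does not move, so the 24-month timetable is unaffected.
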